1.4. Renin-angiotensin system blockers (RASBs)

The role of the renin-angiotensin-aldosterone system in the pathophysiology of hypertension, and cardiovascular and kidney diseases is well known and the renin-angiotensin-aldosterone system is a major regulator of blood pressure through its effect on body fluids and electrolyte homeostasis. For 2 decades, RASBs have been the mainstay of treatment for CKD. Clinical trials have shown that prescription of monotherapy with angiotensin-converting enzyme inhibitors or angiotensin receptor blockers reduces albuminuria and slows the progression of nephropathy in patients with diabetes. In clinical practice guidelines, RASBs are recommended as the antihypertensive drug of choice in patients with CKD with or without diabetes (39,40).

1.5. Overall risk and benefit statement

The major benefit for the IgAN patients enrolled in the present study will be a targeted therapy based on renal lesions described in the kidney biopsy report, given the existing equipoise for scientific studies that may assess the role of kidney biopsy in driving interventions, in light of significant empiric practice evidence and strong, consistent observational evidence supporting a potential causal link.

This may be an advantage for IgAN patients, in line with what is supported by the *MEST-C score* of the Oxford classification validated in the VALIGA study cohort (9).

To date, the current KDIGO guidelines do not consider the presence of active and chronic renal lesions at the time of the kidney biopsy for therapy decision, based on the lack of experimental trial data; this question seems highly relevant in view of pragmatic clinical practice knowledge and the results of cohort studies, their strength and consistency.

The potential risks and benefits of this trial are mainly related to study treatments and they are listed below; the actions/ways to mitigate the risks are specified, in brackets, in the section “Drug risks”.

Drug risks

Corticosteroids: hypertension (anti-hypertensive drugs), water retention (diuretics), hyperglycemia (antidiabetic drugs or insulin), muscle hypotrophy (daily exercise), hyperlipidemia (lipid-lowering agents), body weight increase (diet).

RASBs: allergy (anti-allergy drugs or low doses of corticosteroids), angioedema (corticosteroids), hypotension (dose reduction), hyperkalemia (diet or cation exchange resins), impairment of the renal function (dose reduction or temporary suspension), acute renal failure (drug suspension).

Dapagliflozin: allergy (anti-allergy drugs or low doses of corticosteroids), hyperlipidemia (lipid-lowering agents), hypoglycemia (drug suspension), impairment of the renal function (dose reduction or temporary suspension), acute renal failure (drug suspension).

Drug benefits

Proteinuria reduction, time-averaged proteinuria (TA-P) improvement, proteinuria slope reduction, eGFR slope reduction, delayed end-stage kidney disease.

2. OBJECTIVES

In our CLlGaN study we plan to evaluate:

2.1 Primary objectives

- To evaluate the therapeutic effect on proteinuria with early corticosteroid therapy, administered after the kidney biopsy in IgAN patients with active renal lesions (AClGaN) versus standard care of RASBs alone followed by corticosteroids combined with RASBs;
- To evaluate the therapeutic effect of SGLT2i (Dapagliflozin) combined with RASBs on proteinuria versus corticosteroids combined with RASBs in patients with chronic or moderate renal lesions (CHRONlGaN); thus, to avoid the potential side effects of corticosteroid therapy.

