1.2. Rationale

In our CLlIgAN study, we have planned to evaluate:

- (i) The effect of early start corticosteroid therapy combined with RASBs (experimental arm) versus RASBs alone in IgAN patients with active renal lesions (AClIgAN) who will receive corticosteroids after 4 months of RASBs (standard care) in presence of persistent proteinuria ≥ 0.5 g/24 hours and eGFR ≥ 30 ml/min/1.73 m² (control arm).
- (ii) The effect of SGLT2i (dapagliflozin) combined with RASBs (experimental arm) versus corticosteroids combined with RASBs (control arm) in IgAN patients with chronic or moderate renal lesions (CHRONlIgAN) after a run-in phase of 4 months in which they will receive RASB therapy alone (standard care).

In both studies patients enrolled in the control arms will be treated according to the evidence-based recommendations (standard care) provided within the KDIGO guidelines.

In conclusion, we would like to evaluate the effect of early start corticosteroids in IgAN patients with active renal lesions (AClIgAN) and to spare corticosteroids therapy in IgAN with chronic or moderate renal lesions (CHRONlIgAN) administering Dapagliflozin.

We would also provide earlier ESKD risk prediction by using our tool DialCheck (32).

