4.4 Outcome measures

The primary endpoint is the 24 h-proteinuria reduction between arms as suggested by Inker LA et al (44). It will be assessed after 4 and 8 months in the ACiGaN study and after 10 months in the CHRONiGaN trial.

The secondary end point is the GFR slope calculated as the mean of individual slope obtained from individual linear regression of eGFR overtime (3 years). Based on the International Consensus definition of clinical trial outcomes for kidney failure (23) we have also considered other secondary end points listed below.

Primary and secondary end points that will be evaluated in the two RCTs are listed below:

Primary endpoint:

- Between-arms difference in proteinuria reduction within 4 and 8 months in ACiGaN and within 10 months in CHRONiGaN study.

Secondary endpoints:

- eGFR slope calculated as mean of individual slope obtained from individual linear regression of eGFR overtime (3 years);
- eGFR decline > 40 % from the baseline value;
- composite end point: GFR decline > 40%, ESKD (defined as long-term GFR \leq 15 ml/min/1.73m² for more than three months or need for maintenance dialysis or kidney transplantation) or death due to kidney disease;
- absolute difference between last GFR value and baseline GFR;
- stable renal function defined as a decline in GFR \leq 5 ml/min/1.73m² at the end of three years follow-up;
- mean annual change in the slope of the reciprocal of serum creatinine concentration;
- time-averaged proteinuria (TA-P) calculated as the weighted mean of all post-randomization measurement, with weights representing the time elapsed since the previous measurement;
- proteinuria slope, calculated as a mean of individual slope, obtained from individual linear regression of daily proteinuria overtime (3 years);
- complete remission of proteinuria defined as achievement of urinary protein level \leq 0.2 g/day or a urinary protein-to-creatinine ratio \leq 0.2 g/g;
- partial remission of proteinuria defined as achievement of a urinary protein reduction \geq 50% or greater compared with baseline value.

The end points will be evaluated monthly in IgAN patients with active renal lesions in the first eight months after kidney biopsy and then every three months. In IgAN patients with chronic or moderate renal lesions the end points will be evaluated every three months in the first two years after the enrollment and then every six months.

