5.1 Safety parameters

5.1.1 Definition of adverse events

The International Conference on Harmonization (ICH) Guideline for Good Clinical Practice (GCP) E6(R2) defines an adverse event (AE) as:

Any untoward medical occurrence in a patient or clinical investigation patient administered a pharmaceutical product and which does not necessarily have a causal relationship with this treatment. An AE can, therefore, be any unfavorable and unintended sign (including an abnormal laboratory finding), symptom, or disease temporally associated with the use of a medicinal product, whether or not considered related to the medicinal product.

An AE includes but is not limited to any clinically significant worsening of a patient's pre-existing condition. An abnormal laboratory finding (including ECG finding) that requires an action or intervention by the investigator, or a finding judged by the investigator to represent a change beyond the range of normal physiologic fluctuation, should be reported as an AE.

AEs may be treatment emergent (i.e., occurring after initial receipt of investigational product) or non-treatment emergent. A non-treatment-emergent AE is any new sign or symptom, disease, or other untoward medical event that begins after written informed consent has been obtained but before the patient has received investigational product.

Elective treatment or surgery or preplanned treatment or surgery (that was scheduled prior to the patient being enrolled into the study) for a documented pre-existing condition, that did not worsen from baseline, is not considered an AE (serious or non-serious). An untoward medical event occurring during the prescheduled elective procedure or routinely scheduled treatment should be recorded as an AE or serious (S)AE.

The term AE is used to include both serious and non-serious AEs.

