5.3.5 Adverse events based on examinations and tests

The results from protocol-mandated laboratory tests and vital signs measurements will be summarized in the Clinical Study Report (CSR). Deterioration as compared to baseline in protocol-mandated laboratory values and vital signs will be reported as AEs if they fulfill any of the SAE criteria or are the reason for discontinuation of treatment with the IPs.

If deterioration in a laboratory value or vital sign will be associated with clinical signs and symptoms, the sign or symptom will be reported as an AE and the associated laboratory result or vital sign will be considered as additional information. Whenever possible, the reporting Investigator will use the clinical rather than the laboratory term (e.g., anemia versus low hemoglobin value). In the absence of clinical signs or symptoms, clinically relevant deteriorations in non-mandated parameters will be reported as AEs.

Any new or aggravated clinically relevant abnormal medical finding at a physical examination as compared with the baseline assessment will be reported as an AE.

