7.4 Harms

Safety information will be collected for the intention-to-treat population by recording severe adverse events (SAEs). Upon confirmation, the severity of the AEs will be evaluated for the procedures conducted, the outcomes and the relationships to the study drugs. The AEs will be reported to the principal investigator who will confer with an independent monitoring committee whose members will not know the trial-group assignment. The monitoring committee will evaluate the trial safety and, independently, will determine any necessary revisions to the trial design and will validate all decisions for continuing the trial.

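### CHRONiGaN is justified by sparing corticosteroid harms, but no listed endpoint measures a harm and the adverse-event rules conflict on which of those harms are recorded

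*Protocol*

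**What the plan says.** **Purpose.** The CHRONiGaN objective in Section 2.1 (repeated in the Synopsis) is the effect of dapagliflozin plus RASBs on proteinuria, compared with corticosteroids plus RASBs. It closes with "thus, to avoid the potential side effects of corticosteroid therapy". Section 1.2 ends on the same aim: "to spare corticosteroids therapy in IgAN with chronic or moderate renal lesions".

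**Endpoints.** The primary endpoint in Section 4.4 is "Between-arms difference in proteinuria reduction within 4 and 8 months in ACiGaN and within 10 months in CHRONiGaN study". The ten secondary endpoints concern kidney function, kidney failure or proteinuria; one, for example, begins "stable renal function defined as a decline in GFR".

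**Expected steroid harms.** Section 1.5 names six corticosteroid risks, each with its countermeasure. The list starts "hypertension (anti-hypertensive drugs), water retention (diuretics), hyperglycemia (antidiabetic drugs or insulin" and goes on to muscle hypotrophy, hyperlipidaemia and weight increase.

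**Recording rules.**
- Section 5.1.1 treats as an AE "An abnormal laboratory finding (including ECG finding) that requires an action or intervention by the investigator".
- Section 5.3.5 says that worsening in tests and vital signs mandated by the protocol "will be reported as AEs if they fulfill any of the SAE criteria or are the reason for discontinuation of treatment with the IPs".
- Section 7.4 says that safety information is gathered "by recording severe adverse events (SAEs".
- Sections 5.3 and 5.3.4 have all AEs recorded, serious or not, from consent to 30 days after last treatment.

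**The concern.** CHRONiGaN is a superiority trial on proteinuria (Section 3). If proteinuria turns out similar in the two arms, much of the argument for dapagliflozin would rest on fewer steroid harms. The Protocol then offers no prespecified harm outcome, and its instructions on what counts as a reportable harm disagree with each other.

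The disagreement falls on the effects that matter here. Hypertension, hyperglycaemia and hyperlipidaemia under prednisone are, by Section 1.5, managed by adding a drug. That is an action by the investigator. It need not be serious, and it need not end study treatment. Two sites could therefore treat the same event in the same way and record it differently, each able to cite the Protocol. In an open-label trial, closer metabolic checking of prednisone patients would add a difference in detection between the arms.

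**Working it through.** There is no figure in the plan to reproduce for this point. The CHRONiGaN sample of 300 is called opportunistic in Section 6 and has no stated effect size, SD or power, and the Protocol gives no AE rates. The check is a count and a side-by-side reading.

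**1. Endpoints (Section 4.4).** One primary endpoint concerns proteinuria. Of the ten secondary endpoints:
- Six concern kidney function or kidney events: eGFR slope, eGFR decline above 40%, the renal composite, absolute GFR change, stable function and reciprocal creatinine.
- Four concern proteinuria: time-averaged value, slope, complete remission and partial remission.

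1 + 6 + 4 = 11 endpoints, of which 0 measure a treatment harm.

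**2. What is scheduled (Figure 2B, Section 4.5).** Serum creatinine, eGFR, daily proteinuria, AEs and concomitant medications are assessed at each post-allocation visit. There is no row for glucose, lipids, weight or blood pressure.

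**3. The six named steroid effects against Section 5.3.5.**

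| Effect (Section 1.5) | Scheduled in Figure 2B? | If not mandated | If treated as mandated |
|---|---|---|---|
| Hypertension | No | AE if clinically relevant | AE only if serious or ends treatment |
| Hyperglycaemia | No | AE if clinically relevant | AE only if serious or ends treatment |
| Hyperlipidaemia | No | AE if clinically relevant | AE only if serious or ends treatment |
| Weight increase | No | AE if clinically relevant | AE only if serious or ends treatment |
| Water retention | No | AE as sign or physical finding | AE as sign or physical finding |
| Muscle hypotrophy | No | AE as sign or physical finding | AE as sign or physical finding |

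The restriction clearly covers 0 of 6. Its upper bound is 4 of 6. The Protocol does not settle which column applies. Figure 2B points to the first, but Section 5.3.5 refers to mandated vital signs and Section 3 sets a blood-pressure target for RASB titration, so a site could reasonably take blood pressure as mandated.

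**4. Consequence under each reading.**
- *Mandated:* Section 5.1.1 makes a laboratory value that led to an added drug an AE. Section 5.3.5 does not, unless it is serious or ends treatment. A site cannot follow both.
- *Not mandated:* the deterioration is an AE, but only where someone measured it. Nothing in Figure 2B makes that equal between arms, and treatment is known to all (Sections 3 and 6.3).

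**5. Section 7.4 against the rest.** It describes collection of SAEs in the intention-to-treat population. Sections 5.3 and 5.3.4 record all AEs, and Section 6.5 defines a separate safety population. Section 7.4 also expands SAE as severe rather than serious, a distinction that Section 5.2.1 insists on. Its next sentences then refer to AEs in general.

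**The case against.** The best defence has four parts.

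**The objective is proteinuria.** The clause on side effects is a rationale attached to it, so the trial can meet its stated objective without a harm endpoint. This stands. A reader might infer that the trial cannot show what it set out to show; the text does not support that.

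**AE collection is broad.** Section 5.3.4 takes spontaneous, elicited and observed events. Section 5.3.5 itself adds symptoms, physical findings and clinically relevant changes in non-mandated parameters. This also stands. It defeats the tempting inference that Section 5.3.5 keeps most steroid harms off the record: that would need glucose, lipids, weight and blood pressure all to be mandated, and Figure 2B schedules none of them. If they were mandated, Section 5.3.5 would still have the values summarised in the study report.

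**The monitoring committee is not blind to non-serious events.** After its SAE sentence, Section 7.4 has AEs reported to the principal investigator, who confers with the committee. So Section 7.4 has a wording conflict and is not proof that ordinary AEs go unseen.

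**Safety tables belong in the SAP.** This is true of table layout. But the endpoint list and the recording rules are fixed in the Protocol, and no later analysis plan can recover events that sites were told not to enter or never tested for.

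**Conclusion.** The point holds as a gap together with a contradiction. The stated reason for the comparison has no measure among 11 endpoints, and Sections 5.1.1, 5.3.5 and 7.4 give three different recording rules. Between 0 and 4 of the 6 named steroid effects fall under the restrictive rule, depending on what counts as mandated. If they are not mandated, ascertainment depends on unscheduled testing, which can differ by arm.

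The harm comparison is weakened but not impossible, because AEs and concomitant medications are recorded at the visits in both arms. It is tempting to express the loss as power for a difference in AE proportions. The Protocol gives neither event rates nor the fraction that would go unrecorded, so any such figure would rest wholly on assumption and none is offered. That testing would actually differ by arm is likewise a risk of the open-label design, not something the Protocol states.

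**What to change.** 1. **Reconcile the recording rules.** Bring Sections 5.3.5 and 7.4 into line with Section 5.1.1, so that any laboratory or vital-sign deterioration requiring action is recorded as an AE in both arms. Let Section 7.4 cover all AEs, analysed in the safety population of Section 6.5.

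2. **Add one CHRONiGaN secondary safety endpoint to Section 4.4.** Use the proportion of patients with at least one of the six corticosteroid effects listed in Section 1.5 (hypertension, water retention, hyperglycaemia, muscle hypotrophy, hyperlipidaemia, weight increase) from month 4 to month 10. Count an effect if it is recorded as an AE or by a new or intensified concomitant treatment, and compare the arms. The window matches the six-month prednisone period after the four-month run-in. Show the components separately as well, because some are not specific to steroids: Section 1.5 also lists hyperlipidaemia as a dapagliflozin risk, and antihypertensive use is affected by RASB titration (Section 3) and by dapagliflozin's own effect on blood pressure (Section 1.3).

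**Cost.** Wording in three sections, more non-serious AE entries in the eCRF and one extra between-arm table. The endpoint draws on AE and concomitant-medication records already taken at the Figure 2B visits. It does not remove the problem of unscheduled testing, which should be stated as a limitation.

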2.2 Secondary objectives

- the effect of study treatments on the renal function and on the progression of the kidney damage in IgAN patients at 3 years
- after the prediction of ESKD through our IgAN CDSS tool (DialCheck) at the time of the kidney biopsy, to determine whether personalized therapy delays the impairment of the renal function.

3. TRIAL DESIGN

This project encompasses two prospective, multicentre, open-label randomized controlled clinical trials (RCTs) of IgAN patients (CLlGaN) based on the kidney biopsy report (*Figure 1*).

Stratified randomization will be done by age and sex in renal centers.

[figure not shown]

Figure 1

ACiGaN TRIAL

Patients with active renal lesions (E1 and/or C1) in the presence of $GFR \geq 30$ ml/min/1.73 m² and proteinuria ≥ 0.5 g/24 hours will be randomized into two arms:

- 1) corticosteroids combined with RASBs for 4 months followed by RASBs alone (experimental arm);
- 2) RASBs alone for 4 months followed by the combination corticosteroids and RASBs for 4 additional months and then only RASBs (standard care) as suggested by KDIGO guidelines (5).

Participants assigned to the experimental arm will receive by 2 weeks from the kidney biopsy (pulse) methylprednisolone (SOLU-Medrol) 500-1000 mg in the first day and then 50% of dose in the next two days followed by oral prednisone (0.5 mg/kg/bw) on alternate days until the end of the month. This treatment will be repeated for three consecutive months. After three months, participants will gradually reduce oral prednisone, in the course of four weeks. Next, they will receive RASBs alone.

The daily dose of methylprednisolone will be individualized (15 mg/kg), based on the ideal body weight. The drug will be administered in a single dose intravenously for 30-60 min. To avoid obesity and diabetes corticosteroids will be administered only in the morning.

This is a parallel group, two arm, superiority trial with 1:1 allocation ratio.

As per standard care RASB therapy will be titrated to its maximum labelled or tolerated dose as anti-proteinuric effect in every patient.

Rationale of the study design

Corticosteroids at high dosage have been administered in RCTs of IgAN (18,41) independent of the type of renal lesions despite empiric evidence from clinical practice and strong and consistent evidence from observational studies that the lesions identified at kidney biopsy may play a role in the response to treatment. Our aim is to evaluate the benefit of early pulse therapy combined with oral prednisone only in IgAN patients with active renal lesions. In our protocol, we have excluded intensive immunosuppressive therapy (CS+CYP/AZA/MMF) because RCTs have demonstrated that the potential benefits-harms trade off is in favour of the harms (42).

To our knowledge, this is the first study in which corticosteroids are administered immediately after the kidney biopsy in IgAN patients with active renal lesions. Based on the existing evidence from randomized clinical trials, the KDIGO guidelines suggest in those cases: RASBs for 3-6 months and then corticosteroids in presence of persistent proteinuria and $GFR >30$ ml/min/1.73 m². This therapeutic approach, although supported by evidence, may be a challenge based on empiric clinical knowledge supported also by findings of cohort studies. This demonstrates that after 3-6 months active renal lesions become chronic and consequently no association may be found between exposure to corticosteroids and clinical response for IgAN patients. In our randomized clinical study we compare the standard approach proposed by KDIGO guidelines (RASBs for 3-6 months followed by corticosteroids) vs a novel approach consisting of early corticosteroid therapy combined with RASBs from the beginning.

CHRONIgAN TRIAL

Patients with chronic (T1,2) or moderate renal lesions (M0,1; S0,1, E0, C0, T0) will be enrolled in a two-arm trial with 1:1 allocation ratio to compare Dapagliflozin combined with RASBs (experimental arm) versus corticosteroids combined with RASBs (control arm) after 4 run-in months of RASBs treatment. The enrolled patients will have proteinuria ≥ 0.5 g/day and GFR ≥ 30 ml/min/1.73 m².

Participants will receive study treatments by 4 weeks from the kidney biopsy.

Patients assigned to the experimental arm will receive RASBs therapy (4 run-in months) followed by Dapagliflozin (10 mg /day orally) combined with RASBs for a total of 32 consecutive months. Patients assigned to the control arm will receive RASBs therapy (4 run-in months) followed by oral corticosteroids therapy (prednisone) for six months (0.4 mg/kg body weight for 2 months and then gradual reduction of 5 mg/day for 4 months) and then RASBs alone for a total of 36 consecutive months.

This is a parallel group, two arm, superiority trial with 1:1 allocation ratio.

Rationale of the study design

We decided the combination Dapagliflozin and RASBs because recently, SGLT2is were administered in patients with type 2 diabetes and in other participants with CKD (some of them were affected by IgAN) (29-31). In these studies, the effect of SGLT2is was compared with a placebo.

In our RCTs oral RASBs will be titrated to their maximum anti-proteinuric effect. For example, Ramipril will be administered at a dose of 2.5 mg/day and then increased of 1.25 mg/day every 2 weeks to reduce proteinuria to 0.5 g/day or less and to achieve a systolic and diastolic pressure of $<130/80$ mmHg. We will monitor the outcomes to look at whether the experimental therapy may delay the time to reach the ESKD predicted by our IgAN tool DialCheck (32)

Patients will be converted to angiotensin receptor blockers (ARB) in presence of ACE-inhibitors (ACEi) intolerance for side effects. Ramipril will be administered two times a day (8 am and 8 pm) to control blood pressure. If necessary other anti-hypertensive drugs will be administered. Kalemia will be controlled so as not exceed 5.5 mEq/L.

In conclusion, we have designed two RCTs to study targeted therapy in biopsy-proven IgAN patients.

